### 5.5.2. Analysis Methods

Analyses of the other endpoints will be performed on the ITT population, unless otherwise specified. Analysis of time-to-event endpoints and endpoints with binary outcome will be carried out as described above (see start of Section 5).

### 5.5.3. Patient Reported Outcome (PRO) and Analgesics Use

A separate statistical analysis plan will be provided for PRO data.

## 6. SAFETY

### 6.1. Adverse Events

Subjects will be assessed for AEs at each monthly clinic visit while on the study. Adverse events will be graded according to the NCI-CTCAE Version 4.03 and coded to preferred term and system organ class (SOC) using the most recent version of MedDRA.

All AEs reported during the AE reporting period (inclusive of the 30-day post last dose of study drug period) will be considered as treatment-emergent adverse events and will be summarized by treatment group as treated using all subjects in the safety population.

For each treatment group, AE incidence rates will be summarized with frequency and percentage by SOC and preferred term, with all subjects treated in that treatment group as the denominator, unless otherwise specified. In addition, AE incidence rates will also be summarized by severity and relationship to study drug. Treatment-related AEs are those judged by the Investigator to be at least possibly related to the blinded study drug. Subjects with multiple occurrences of events will only be counted once at the maximum severity to study drug for each preferred term, SOC, and overall. Deaths that occur within 30 days after the last dose of study drug are defined as on-study deaths.

AE onset date will not be imputed if it's completely missing. Partial AE onset date will be imputed as follows:

- If the AE onset date is missing day only, it will be set to:
  - the first day of the month that the AE occurred, if the month/year of the onset of AE is different from the month/year of the study treatment start;
  - the day of the study treatment start, if the month/year of the onset of AE is the same as month/year of the study treatment start but different from the month/year of the AE resolution date;

- the day of the study treatment start or the day of AE resolution date, whichever is earlier if the month/year of the onset of AE and month/year of the study treatment start and month/year of the AE resolution date are same;
- If the AE onset date is missing both day and month, it will be set to the earliest of:
  - January 1 of the year of onset, as long as this date is after the study treatment start;
  - the day and month of the study treatment start, if this date is the same year as that the AE occurred;
  - the AE resolution date.

Summary tables of the following AEs will be provided:

- Overall summary of AEs: the number and percentage of subjects who experienced any AE, any serious adverse event (SAE), any treatment-related AE, any treatment-related SAE, any discontinuations due to an AE, and any deaths
- All AEs by SOC and preferred term All AEs by SOC, preferred term, and toxicity grade
- Grades 3 or 4 AEs by SOC and preferred term
- Treatment-related AEs by SOC and preferred term
- Treatment-related AEs by SOC, preferred term, and toxicity grade
- Treatment-related Grades 3 or 4 AEs by SOC and preferred term
- AEs that led to study drug discontinuation by SOC and preferred term. Study drug discontinuation will be determined from the treatment disposition CRF (where reason for discontinuation is “Adverse Event”) and the specific AE will be determined from the AE CRF page (where action taken is “Drug withdrawn”)
- AEs that led to study drug discontinuation by SOC, preferred term, and toxicity grade
- AEs that led to dose modification by SOC, preferred term, and toxicity grade
- All SAEs by SOC and preferred term
- All SAEs by SOC, preferred term, and toxicity grade
- Deaths will be summarized by time period (on-study vs. during follow-up) and cause of death.

Subject listings of all AEs by toxicity grade, Grades 3 or 4 AEs, all SAEs, AEs that led to study drug discontinuation, dose modification, and all deaths will be provided as well.

Narratives will be written for the following subjects in the final clinical study report:

- Subjects who die  $\leq 30$  days after the last dose of study drug
- Subjects who discontinue study drug due to treatment-emergent AE
- Subjects who experience a treatment-emergent SAE
- Subjects who experience seizure
- Subjects who experience Grade 3 or higher treatment-emergent major adverse cardiovascular events (MACE) including ischemic heart disease, cardiac failure, cerebrovascular disease, and arrhythmias
- Subjects who experience treatment-emergent primary cancers

Subjects who experience other Grade 3 or higher treatment-emergent adverse events of special interest.

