11.7. Safety Analyses

The safety parameters to be evaluated are the incidence, intensity, and type of AEs, vital signs (blood pressure), ECG, and clinical laboratory results. Exposure to study drug and reasons for discontinuation of study treatment will be tabulated.

Adverse Events

The verbatim terms used in the eCRF by investigators to identify AEs will be coded using the most current Medical Dictionary for Regulatory Activities (MedDRA) and will be graded according to NCI-CTCAE (Version 4.03). Treatment-emergent AEs are AEs that occur or worsen on or after first dose of study drug through 30 days after the last dose of study drug and will be included in the analysis. Adverse events will be summarized by system organ class and preferred term, and will be presented overall and by treatment group. Serious adverse events and deaths will be provided in a listing. All AEs resulting in discontinuation, dose modification, dosing interruption, or treatment delay of study drug will also be listed and tabulated by preferred term.

Clinical Laboratory Tests

Clinical laboratory test results will be collected from Screening and through 30 days after last dose of study drug. Laboratory data will be summarized by type of laboratory test. Parameters with predefined NCI-CTCAE (Version 4.03) toxicity grades will be summarized. Change from baseline to the worst AE grade experienced by the subject during the study will be provided as shift tables.

Electrocardiogram (ECG)

Electrocardiogram data obtained at screening will be summarized by ECG parameter.

Vital Signs

Descriptive statistics of blood pressure (systolic and diastolic) values and changes from baseline will be summarized at each scheduled time point. The percentage of subjects with values beyond clinically important limits will be summarized.

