12.1. Definitions

12.1.1. Adverse Event Definitions and Classifications

Adverse Event

An AE is any untoward medical occurrence in a clinical study subject administered a medicinal (investigational or non-investigational) product. An AE does not necessarily have a causal relationship with the treatment. An AE can therefore be any unfavorable and unintended sign (including an abnormal finding), symptom, or disease temporally associated with the use of a medicinal (investigational or non-investigational) product, whether or not related to that medicinal (investigational or non-investigational) product. (Definition per International Conference on Harmonisation [ICH])

This includes any occurrence that is new in onset or aggravated in severity or frequency from the baseline condition, or abnormal results of diagnostic procedures, including laboratory test abnormalities.

Note: The sponsor collects AEs starting with the signing of the ICF (refer to Section [12.3.1](#) for time of last AE recording).

Serious Adverse Event

A serious AE based on ICH and EU Guidelines on Pharmacovigilance for Medicinal Products for Human Use is any untoward medical occurrence that at any dose:

- Results in death
- Is life-threatening
(The subject was at risk of death at the time of the event. It does not refer to an event that hypothetically might have caused death if it were more severe)
- Requires inpatient hospitalization or prolongation of existing hospitalization
- Results in persistent or significant disability/incapacity
- Is a congenital anomaly/birth defect
- Is a suspected transmission of any infectious agent via a medicinal product
- Is medically important*

*Medical and scientific judgment should be exercised in deciding whether expedited reporting is also appropriate in other situations, such as important medical events that may not be immediately life-threatening or result in death or hospitalization but may jeopardize the subject or may require intervention to prevent one of the other outcomes listed in the definition above. These should usually be considered serious.

Unlisted (Unexpected) Adverse Event/Reference Safety Information

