12.3. Procedures

12.3.1. All Adverse Events

All AEs and special reporting situations, whether serious or non-serious, will be reported from the time a signed and dated ICF is obtained until 30 days after the last dose of study drug. Serious adverse events, including those spontaneously reported to the investigator within 30 days after the last dose of study drug, must be reported using the Serious Adverse Event Form. The sponsor will evaluate any safety information that is spontaneously reported by an investigator beyond the time frame specified in the protocol.

All events that meet the definition of an SAE will be reported as SAEs, regardless of whether they are protocol-specific assessments. Anticipated events will be recorded and reported as described in [Attachment 4](#). Some countries will not identify anticipated events for the Health Authorities.

All AEs, regardless of seriousness, severity, or presumed relationship to study drug, must be recorded using medical terminology in the source document and the eCRF. Whenever possible, diagnoses should be given when signs and symptoms are due to a common etiology (eg, cough, runny nose, sneezing, sore throat, and head congestion should be reported as "upper respiratory infection"). Investigators must record in the eCRF their opinion concerning the relationship of the AE to study therapy. All measures required for AE management must be recorded in the source document and reported according to sponsor instructions.

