### **1.2. Study Design**

This is a randomized, double-blind, placebo-controlled, multinational, multicenter Phase 3 study to determine if subjects with mHSPC will benefit from the addition of apalutamide to ADT. Enrollment of approximately 1,000 subjects is planned for this study. Subjects who meet all of the inclusion criteria and none of the exclusion criteria will be stratified by Gleason score at diagnosis, prior docetaxel use, and geographic region, and then randomly assigned in a 1:1 ratio to the apalutamide plus ADT or matching placebo plus ADT group.

The study will include a Screening Phase of up to 28 days before randomization to establish study eligibility. Subjects will receive treatment in 28-day treatment cycles during the Treatment Phase until

disease progression or the occurrence of unacceptable treatment-related toxicity. Subjects must discontinue study drug with documented clinical progression. After discontinuation of study drug, subjects will have an End-of-Treatment Visit within 30 days after the last dose of study drug. In the event of a positive study result at either of the interim analyses or at the final analysis, all subjects in the Treatment Phase will have the opportunity to enroll in an Open-label Extension Phase, which will allow subjects to receive active drug (apalutamide) for up to 3 years.

Subjects will be monitored for safety starting from the signing of informed consent until 30 days after the last dose of study drug. Adverse events including laboratory AEs will be graded and summarized using the National Cancer Institute Common Terminology Criteria for Adverse Events (NCI-CTCAE) Version 4.03. Dose modifications will be made as required according to dose modification rules. An Independent Data Monitoring Committee (IDMC) will be commissioned for the study to provide recommendation during the planned interim efficacy analysis and regular safety review.

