### 2.1. Visit Windows

The Treatment Phase will begin at Cycle 1 Day 1 of treatment and will continue until study drug is discontinued. Study treatment should be initiated (Cycle 1 Day 1) within 3 calendar days after randomization. Visits for each cycle will have a  $\pm 2$  day window except for computed tomography (CT)/magnetic resonance imaging (MRI) and bone scans (imaging visits may occur up to 8 days before scheduled cycles).

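### SAP 6.1 gives treatment-emergent AEs no first-dose start, so as written it admits up to 31 days of pre-dose events that protocol 11.7 excludes

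*SAP*

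**What the plan says.** The two documents define a treatment-emergent AE differently.

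- Protocol 11.7: "Treatment-emergent AEs are AEs that occur or worsen on or after first dose of study drug through 30 days after the last dose".
- SAP 6.1: all "AEs reported during the AE reporting period (inclusive of the 30-day post last dose of study drug period) will be considered as treatment-emergent" events. This states when the period ends but not when it begins, and it sets no condition on onset relative to first dose.

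The SAP does not define the AE reporting period anywhere else. Where the documents do give a start for AE collection, it is consent:

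- Protocol 12.3.1: AEs "will be reported from the time a signed and dated ICF is obtained until 30 days after the last dose of study drug".
- Protocol 12.1.1: "The sponsor collects AEs starting with the signing of the ICF".
- SAP 1.2: "Subjects will be monitored for safety starting from the signing of informed consent until 30 days after the last dose of study drug".
- The protocol's Time and Events Schedule shows AE collection as continuous over the same span.

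The time between consent and first dose is bounded by a "Screening Phase of up to 28 days before randomization" and by the rule that treatment starts "within 3 calendar days after randomization".

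**The concern.** An event that begins and ends before the first tablet cannot be treatment-emergent. A programmer who works from SAP 6.1 alone would apply no onset condition. Pre-dose events of dosed men would then enter the all-cause AE, Grade 3-4 and serious AE tables, and would trigger narratives that depend on treatment-emergence, mainly those for serious AEs. The exploratory exposure-adjusted rates in SAP Attachment 1 use the first event per patient and the exposure time up to it, so they would also take in events that precede exposure.

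The stakes are limited to safety reporting. Efficacy analyses and type I error do not depend on this definition.

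**Working it through.** **1. Does any SAP text remove pre-dose events?** These are the candidates:

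- *Safety population (SAP 2.3):* requires at least one dose. It selects men, not events, so a dosed man keeps his pre-dose AEs.
- *Study Day (SAP 2):* safety Study Day 1 is the first dose. This numbers days and filters nothing.
- *Treatment period (SAP 4.5):* runs from first dose to 30 days after the last dose, but is stated for concomitant medication only.
- *Status of the SAP (SAP 1):* it supplements the protocol. That points to intent, but no clause says which text prevails when the two differ.

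None of these is a filter on AEs. In the other direction nothing is lost: the SAP rule is broader than the protocol rule, so AEs that worsen on treatment are still counted.

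**2. Length of the window.** The documents state no figure for it. From their own limits, 28 + 3 = 31 days, against 0 days under protocol 11.7. Both terms are maxima. The sum is 28 days if dosing starts on the day of randomization. The Time and Events Schedule also allows imaging within 6 weeks of randomization; if one assumes consent was signed before study-specific imaging at that limit, the sum is 42 + 3 = 45 days.

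**3. Illustrative size.** The documents give no pre-dose AE rate, so the following inputs are assumptions: one AE term with on-treatment incidence q of 20% (apalutamide) and 15% (placebo) over 20 months, about 500 men per arm (1,000 at 1:1), and the placebo hazard acting before dosing in both arms.

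- Baseline: risk ratio (RR) 20/15 = 1.33; risk difference 5.0 points.
- Placebo hazard: -ln(0.85)/20 = 0.8126 per 100 person-months.
- Window: 31/30.44 = 1.018 months.
- Pre-dose probability: p = 1 - exp(-hazard x time).
- Incidence under the SAP rule: 1 - (1 - q)(1 - p).

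| Pre-dose scenario | p | Apalutamide | Placebo | RR | Difference (points) |
|---|---|---|---|---|---|
| None (protocol 11.7) | 0 | 20.00% | 15.00% | 1.333 | 5.00 |
| Half the window (15.5 days) | 0.413% | 20.33% | 15.35% | 1.324 | 4.98 |
| Full 31 days | 0.824% | 20.66% | 15.70% | 1.316 | 4.96 |
| 31 days, twice the hazard | 1.642% | 21.31% | 16.40% | 1.300 | 4.92 |

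The full-window case adds about 500 x 0.00824 = 4.1 men with a pre-dose event per arm.

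**4. Attachment 1.** Section 3.3 sets the patient's rate as 1/t, where t is the time of the first event. Counted from first dose, a pre-dose onset gives a negative t and a negative rate; if t is cut off at zero, the rate is undefined. The pooled rates in sections 3.4 to 3.6 are sums and can still be computed. With hazard λ = -ln(1 - q)/20 and zero time for pre-dose events, the pooled rate is (p + (1 - p)q) / ((1 - p)q/λ). The ratio is 1.116/0.813 = 1.373 with no pre-dose events and 1.162/0.858 = 1.355 for the full window (1.364 and 1.339 for the other two scenarios).

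**The case against.** The strongest reply is that this is loose drafting with an obvious meaning. The protocol has an express definition, the SAP supplements the protocol, safety days count from first dose, and SAP 4.5 uses the same span as protocol 11.7 for its treatment period. A programmer holding both documents would probably apply the protocol rule. This stands as evidence of intent, and it means one cannot predict that pre-dose events would in fact be tabulated. It does not remove the conflict: SAP 6.1 is an explicit rule, and it yields a different count from the protocol.

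A reader might infer more than the documents support in four ways:

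- *That the partial-date rules prove pre-dose events are counted.* When onset, treatment start and resolution share a month, onset becomes "the day of the study treatment start or the day of AE resolution date, whichever is earlier". This can give a pre-dose date, but its plain purpose is to keep onset from falling after resolution, and such a date is also what would let an analyst exclude the event. The rule is neutral.
- *That 31 days is a fixed or typical period.* It is the sum of two maxima.
- *That one arm is favored.* The events precede any study drug, and most precede randomization, so they are balanced in expectation.
- *That every safety output is affected.* Treatment-related, discontinuation, dose-modification, death and seizure outputs are largely protected by their own criteria. Most cardiovascular or other-cancer events before randomization would make a man ineligible under protocol 4.2, so those narratives change little.

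The objection that the numerical illustration is not drawn from the documents is also correct. It shows scale only.

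**Conclusion.** SAP 6.1 is wrong as written, and the matter is minor. Taken literally, it contradicts protocol 11.7 and admits AEs of dosed men from up to 31 days before first dose. The result would be a small, non-differential rise in all-cause, Grade 3-4 and serious AE incidence, and some narratives that are not needed. The true size cannot be determined from the documents. On the assumed rates above, the risk ratio moves from 1.33 to between 1.32 and 1.30 and the risk difference by less than 0.1 point, which would not change a safety conclusion. In Attachment 1 the pooled rates barely move, but the per-patient rate has no sensible value for a pre-dose onset.

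The textual conflict is certain. Whether pre-dose events would really reach the tables depends on how the SAP is programmed, and the surrounding text suggests that this was not intended.

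**What to change.** Replace the SAP 6.1 sentence with the protocol 11.7 definition. Apply it to the AE incidence tables, to the narratives triggered by treatment-emergence, and to the Attachment 1 rates. Keep pre-dose AEs in the all-AE listings that SAP 6.1 already plans, and out of the tables.

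The cost is one SAP sentence and a date condition in the AE programs. One point needs checking first. The worsening part of the definition requires a way to date a change in grade, and protocol 9.6 specifies grade-onset values for laboratory AEs only. The sponsor should confirm how the eCRF records worsening of other AEs. Which time Attachment 1 should use for an AE that began before dosing and worsened later is a separate choice, which protocol 11.7 does not settle; the SAP should state it.

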(PFS2) was longer for the apalutamide arm (not estimable) compared with the placebo arm (39 months). There was a 51% reduction in the risk of disease progression during first subsequent therapy or death (PFS2) for subjects originally assigned to the apalutamide + ADT arm compared with the placebo + ADT arm (HR=0.489; 95% CI: 0.361, 0.662; p<0.0001). Patient-reported outcome results indicated that there was no detriment to overall health-related quality of life with the addition of apalutamide to ADT. Similar mean changes from baseline or median time to worsening in the Functional Assessment of Cancer Therapy-Prostate (FACT-P) were observed in the 2 arms. For nearly all time points, no differences between apalutamide and placebo were observed in change from baseline across the EQ-5D index or visual analog scale.

The 3 most frequently reported TEAEs were fatigue, hypertension, and skin rash as a grouped term. Most events of skin rash were Grade 1 or Grade 2 and responded to administration of antihistamines and topical steroids; dose reduction and interruptions were also used to manage skin rash. Similarly, fatigue was mostly Grade 1 or Grade 2 which suggest that the fatigue associated with apalutamide treatment was not disabling or severe enough to interfere with activities of daily living. After adjusting for exposure, hypertension was similar in both arms and was not considered attributable to apalutamide. Fracture as a grouped term was the most commonly reported SAE, and considered serious because fracture in this elderly population often requires hospitalization. Ten percent of subjects in the study used bone-sparing agents such as bisphosphonates and denosumab. In addition to skin rash and fracture, AEs of special interest for apalutamide included fall, hypothyroidism (which was discovered since TSH was regularly monitored in Study ARN-509-003), and seizure. In Study ARN-509-003, 40% to 50% of the fractures reported in both arms were preceded by a fall (another AE of special interest) within 7 days; falls were not typically preceded by syncope or presyncope, but may have been associated with weight loss, weakness, or dizziness/vertigo. When adjusted for exposure, it appeared that apalutamide in combination with ADT did not have a clinically meaningful increase in the incidence of TEAEs compared with subjects who received ADT alone.

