9.1.3. Treatment Phase

The Treatment Phase will begin at Cycle 1 Day 1 of treatment and will continue until study drug is discontinued. Subjects should start study drug within 3 calendar days after randomization. Visits for each cycle will have a ± 2 -day window except for CT/MRI and bone scans (imaging visits may occur up to 8 days before cycles). Study visits will be calculated from the Cycle 1 Day 1 date. Please refer to the Time and Events Schedule for treatment visits and assessments during the Treatment Phase. The last measurements taken on Day 1 of Cycle 1 before administration of study drug or at screening (whichever value was last) will be defined as the baseline values.

After the PRO questionnaires have been administered, a symptom-directed physical exam and laboratory testing scheduled for the same visit will be conducted. Adverse events and changes to concomitant medications will be recorded. Subjects will be evaluated throughout this phase for possible toxicities. Dose modifications for toxicity will be made as according to criteria described in Section 6.3.

During the Treatment Phase, investigators will review all clinical, laboratory and imaging data, and will use this information to make decisions about dose modification and study medication discontinuation. Clinical evaluations and laboratory studies may be repeated more frequently, if clinically indicated. The subject should refrain from taking study drugs on the morning of study visits designated for trough PK sampling until seen at the site. Treatment will continue until disease progression or the occurrence of unacceptable treatment-related toxicity. If the subject has radiographic progression without clinical progression and alternate therapy is not initiated, treatment may continue at the discretion of the investigator. Subjects must discontinue treatment if clinical progression is documented (see Section 10.2). Once the subject discontinues study drug, the subject will complete the End-of-Treatment (EOT) Visit.

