### **1.4. Sample Size Justification**

An overall type I error of 5% is planned for this study. This study utilizes the dual-primary endpoints of rPFS and OS with a 0.005 level of significance allocated for the rPFS endpoint and 0.045 is allocated for OS.

It is assumed that the failure distribution of the dual-primary endpoint of rPFS follows an exponential distribution with a constant hazard rate. It is estimated that approximately 368 rPFS events would be required to provide at least 85% power in detecting a hazard ratio (HR) of 0.67 (median rPFS of 20 months for the control group [ADT] versus 30 months for the treatment group of apalutamide plus ADT) at a 2-tailed significance level of 0.005. The assumption of 20 months for the control is an estimate based on published data.

The study will also provide sufficient power (approximately 80%) to detect a HR of 0.75 in the dual-primary endpoint of overall survival (OS) based on an assumed OS median of 44 months for the control group (ADT) (i.e., 44 months versus 59 months). Approximately 410 death events will be required to detect the assumed HR at a 2-tailed significance level of 0.045 with enrollment duration of

approximately 30 months (approximately 1,000 subjects). The total study duration will be approximately 54 months to obtain 410 deaths.

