## **ATTACHMENT 1: ADDITIONAL EXPLORATORY ANALYSIS TO SUPPORT HEALTH ECONOMICS, MARKET ACCESS AND REIMBURSEMENT (HEMAR)**

### **1. DEFINITION OF SUBGROUPS**

Analysis will be performed to determine whether the treatment effect is consistent among subgroups. Analysis will be conducted for the ITT population and for the following subgroups

- For subjects that are considered high risk defined as having two of the three following high-risk factors associated with poor prognosis:
  - A Gleason score of 8 or more on a scale of 2 to 10, with higher scores indicating more aggressive disease
  - At least three bone lesions
  - The presence of measurable visceral metastasis.
- For subjects not fulfilling high risk criteria and considered low risk

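### SAP 6.1 reports adverse events only as crude percentages, although the length of AE collection follows time on drug and may differ between the arms

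*SAP*

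**What the plan says.** - **Measure.** SAP 6.1 has AE incidence "summarized with frequency and percentage by SOC and preferred term, with all subjects treated in that treatment group as the denominator". The listed tables (all AEs, Grade 3 or 4, treatment-related, SAEs, AEs leading to discontinuation or dose modification) specify nothing else. Section 6 contains no person-time, time-to-first-event or cumulative-incidence analysis. SAP 4.3 summarises exposure by arm, but separately from the AE tables.
- **Window.** Protocol 11.7 counts AEs that "occur or worsen on or after first dose of study drug through 30 days after the last dose of study drug". SAP 6.1 likewise takes a reporting period "inclusive of the 30-day post last dose of study drug period".
- **Length of treatment.** Protocol 9.1.3: "Treatment will continue until disease progression or the occurrence of unacceptable treatment-related toxicity". Protocol 9.1.3 and 10.2 also let dosing go on after radiographic progression when there is no clinical progression.
- **Design assumption.** SAP 1.4 assumes a "median rPFS of 20 months for the control group [ADT] versus 30 months for the treatment group of apalutamide plus ADT". Neither document gives an expected treatment duration by arm.
- **Precedent.** On the sponsor's earlier Phase 3 trial (ARN-509-003), Protocol 1.1.2.1 says: "After adjusting for exposure, hypertension was similar in both arms and was not considered attributable to apalutamide". It makes a similar exposure-adjusted statement about TEAEs overall.
- **Attachment 1.** Section 3 of this SAP attachment plans exposure-adjusted first-event rates for TEAEs by preferred term, by SOC and globally. Its title marks it as exploratory and directed at health economics and reimbursement.

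**The concern.** A crude percentage compares arms fairly only if men are watched for similar lengths of time. Here the watching stops shortly after the drug does, and an effective drug would be expected to keep men on treatment longer. The crude difference then mixes drug effect with longer observation.

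An acceptable safety profile is part of the study hypothesis, and characterising safety is a secondary objective. Protocol 1.1.2.1 raises a possible fracture risk with apalutamide and lists rash, fracture, fall, hypothyroidism and seizure as events of special interest, with rash and fracture as grouped terms. For harms that build up over time, the SAP 6.1 tables cannot separate a real excess from longer observation. The kind of analysis on which the sponsor's reading of its earlier trial rested is missing from the main safety section.

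**Working it through.** **Inputs from the documents.** Median rPFS 20 and 30 months, exponential; 368 rPFS events for at least 85% power at HR 0.67 and two-sided 0.005; control median OS 44 months, HR 0.75; about 1,000 men, 1:1, enrolled over 30 months; 205 deaths at the first OS look; 410 deaths at about month 54.

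**Assumptions.** Uniform accrual; dosing stops at the rPFS event; one-month tail; no other dropout; no crossover; the same constant first-AE hazard h in both arms. The documents give no AE rate, so h is varied from 0.005 to 0.05 per month.

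**Reproducing the plan.** Schoenfeld: 4(2.807 + 1.036)²/(ln 0.67)² = 59.1/0.1604 ≈ 369 events; 368 events give 84.9% power. With the plan's inputs, 368 rPFS events fall at month 32.1, 205 deaths at month 32.2 and 410 deaths at month 54.0. The design figures hold together.

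**Crude percentage under no drug effect.** For a man with follow-up c to the cut-off, the AE window is W = min(D + 1, c), with D exponential at rate λ (ln 2/20 = 0.0347 or ln 2/30 = 0.0231). For c > 1,

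P(no AE in W) = [λ/(λ+h)]·e^(−h)·(1 − e^(−(λ+h)(c−1))) + e^(−λ(c−1) − hc).

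Averaging over c uniform on (T − 30, T) gives, placebo versus apalutamide:

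| h per month | Month 32.2 | Ratio | Month 54 | Ratio |
|---|---|---|---|---|
| 0.005 | 6.0% vs 6.6% | 1.10 | 10.1% vs 11.9% | 1.18 |
| 0.01 | 11.6% vs 12.7% | 1.09 | 18.8% vs 22.0% | 1.17 |
| 0.02 | 21.3% vs 23.2% | 1.09 | 32.8% vs 38.0% | 1.16 |
| 0.05 | 42.6% vs 45.8% | 1.07 | 58.2% vs 65.0% | 1.12 |

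Mean windows are 12.6 vs 13.9 months at month 32.2 and 21.8 vs 25.9 at month 54. With the first look at month 31.7, the 0.01 row reads 11.3% vs 12.4%, again a ratio of 1.09.

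**Person-time rate.** Expected time to first event or end of window is P(AE)/h, so events divided by person-time return h in both arms. At h = 0.01 that is 12 per 100 person-years in each, and the gap disappears.

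**Early-onset harm.** With all risk in the first 3 months, the crude figures near month 32 are 5.7% vs 5.7% (h = 0.02) and 13.6% vs 13.6% (h = 0.05).

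**Fixed-time incidence.** If the end of the window counts as a competing event, set c = 12 or 24 with h = 0.01. Placebo at 12 months: 1 − (0.776 × 0.990 × 0.388 + 0.606) = 9.6%; apalutamide 10.1%. At 24 months: 15.2% vs 16.9%. These are ratios of 1.05 and 1.11 with no drug effect. Censoring at the end of the window gives 1 − e^(−0.12) = 11.3% and 1 − e^(−0.24) = 21.3% in both arms.

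**The case against.** Much of the other side's case stands.

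- **A reader might infer that the SAP has no exposure adjustment.** It does, in Attachment 1. The per-preferred-term rates there would cover hypertension, fall and hypothyroidism. What they lack is standing and scope. They are exploratory and not referred to from Section 6. They do not extend to SAEs, Grade 3 or 4 AEs, grouped terms or AEs leading to discontinuation. A between-arm comparison is suggested but not committed to, and no confidence interval is specified. Attachment 1 section 3.2 also ends time at risk for event-free men at total treatment duration, while TEAEs count for 30 further days, so numerator and denominator cover different windows.
- **A reader might infer that the plan expects longer treatment on apalutamide.** It states only rPFS medians. Dosing past radiographic progression could change the gap, and more stopping for toxicity on apalutamide could shrink or reverse it. In the reversed case crude percentages would hide harm, so the remedy is useful in either direction.
- **A reader might infer that any harm of equal risk will look worse on apalutamide.** That applies only to risk that persists through treatment; early-onset harms are barely affected.
- **A reader might infer false safety signals at some error rate.** SAP 6.1 is descriptive and plans no between-arm AE test.
- **Month 54 is not the natural headline.** A positive result at an earlier analysis, followed by unblinding, opens crossover (Protocol 9.1.6). The first-look gap is modest.

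**Conclusion.** The point holds as a limited reporting weakness. SAP 6.1 ties the AE window to time on drug and then reports only crude percentages. If time on drug follows the assumed rPFS medians, a persisting harm with equal hazard looks about 7% to 10% more frequent in relative terms on apalutamide at the first OS look (0.6 to 3.1 percentage points), and 12% to 18% more frequent at month 54 (1.8 to 6.9 points). These sizes rest on rPFS as a stand-in for time on drug, on assumed constant AE hazards and, for month 54, on blinded treatment continuing without crossover.

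The documents do not support saying that the SAP ignores exposure altogether, or that every harm will be exaggerated. They do support moving the exposure-adjusted analysis into the main safety section and widening it.

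**What to change.** In SAP 6.1, beside the crude percentages:

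1. Report by arm the first-event rate per 100 person-years, with a between-arm contrast and 95% CI, for TEAEs, Grade 3 or 4 AEs, SAEs, AEs leading to discontinuation and grouped AEs of special interest.
2. End time at risk at the first event, the end of the TEAE window including the 30-day tail, or the data cut-off, whichever comes first.
3. Cross-refer to Attachment 1 and align its time at risk with that definition.
4. If incidence at fixed times is added (for example 12 and 24 months), censor at the end of the TEAE window and treat death as competing. Do not make the end of the window a competing event in the main version, because that keeps the exposure artefact.

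The cost is some SAP wording and a few tables from AE onset and dosing dates already collected; no visits or patients are added. Two limits should be stated: person-time rates assume a roughly constant hazard, and censoring at the end of treatment assumes that stopping is non-informative.
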